Forty-one patients were consented and enrolled as participants. Thirteen (31.7%) of the participants did not complete this investigation for the following reasons: seven requested pharmacological intervention during the experimental period and were withdrawn, one was diagnosed with Rocky Mountain Spotted Fever and withdrawn, and five were lost to follow-up. Twenty-eight participants (68.3%) completed the investigation. Analysis was performed for the 28 participants with completed data sets. Mean age was 46.4 years (standard deviation = 16) and participants were 78.6% female.

Study Materials

Participants completed the Dizziness Handicap Inventory (DHI), Headache Disability Inventory (HDI), and lifestyle scale (Table 1) prior to and again after lifestyle modification intervention. The DHI and HDI are 25-item self-report tools that examine impact of dizziness symptoms and headache symptoms on HRQOL. Lower total scores indicate less impact of the symptoms on HRQOL. The lifestyle scale was developed for this study to gain an understanding of self-perceived restful sleep, mealtime regularity, exercise, and avoidance of dietary triggers. Participants indicated their level of agreement with each statement using a 5-point Likert scale. Higher scores indicated better self-perceived compliance with the lifestyle component.

Procedures

Data were collected either paper/pencil or using an online Redcap survey, depending on participant preference and in-person COVID-related limitations. Participants completed the DHI, HDI, and lifestyle scale during a clinic appointment before and after the intervention. On average, participants completed post-intervention surveys after 105 days (standard deviation = 78.1).

Intervention

The intervention addressed four areas related to lifestyle modification that have been shown to be effective in at least some patients with VM or with migraine. These areas were restful sleep, mealtime regularity, exercise, and elimination of dietary triggers. The diagnosing clinicians provided a four-page handout (see supplemental digital content) with information about each area after their diagnosis and after the patient completed the informed consent process.

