For restful sleep, we provided helpful tips adapted from the National Institute on Aging. To bring focus to mealtime regularity, the handout provided informational statements that skipping or missing meals can lead to symptoms and the participant should prepare ahead to ensure they are eating on a schedule. We also encouraged participants to continue or resume a preferred exercise program or start some type of formal exercise. A sample walking program from the National Heart, Lung, and Blood Institute²⁵ was adapted and provided along with the caveat to only begin such a program if medically cleared. Finally, we combined information from published research¹⁶ and other publicly available resources to develop a comprehensive elimination list of potential dietary triggers. Participants were asked to follow this four-part intervention until follow-up, with an initial goal of at least 60 days.

Statistical Methods

Scores on the lifestyle scale were analyzed using linear mixed-effects models with two within-participant factors, Intervention (pre-intervention, post-intervention) and Lifestyle Factor (restful sleep, exercise, mealtime regularity, avoiding dietary triggers).

Scores on the two handicap inventories, DHI and HDI, were also analyzed using linear mixed-effects models with two within-participant factors, Intervention (pre-intervention, post-intervention) and Inventory (DHI, HDI). For all models, participant was included as a random factor. Models were constructed using the *lmer* function of the *lme* package in R and were analyzed using the *anova* function in base R. Significant main effects and interactions were evaluated using the *emmeans* function of the *emmeans* package. Pairwise comparisons were adjusted to account for false-discovery rates.

Inter-individual variability in pre- to post-intervention scores were analyzed by calculating change scores (subtracting post-intervention from pre-intervention scores [DHI and HDI] or subtracting pre-intervention from post-intervention scores [lifestyle scale]). Two linear mixed models were constructed, one for each inventory, with the change scores as the dependent variable. Independent variables were participant sex, age, and lifestyle change score for each lifestyle question. Models were constructed and analyzed with the *lmer* and *anova* functions, respectively.

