Finally, to determine individual participant post-intervention change, we compared pre- and post-total scores for the DHI and HDI. On the DHI, a change of 18 points is considered significant. For the HDI, a change of 29 points is considered significant.

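### The DHI and HDI change-score models are analysed by anova alone, so the lifestyle terms get no direction, slope or interval, and with 28 participants most non-significant terms would be inconclusive

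*Combined protocol and SAP*

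**What the plan says.** The models at issue are in the paragraph of Statistical Methods on inter-individual variability (combined protocol and SAP):

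- Outcome: "Two linear mixed models were constructed, one for each inventory, with the change scores as the dependent variable". DHI and HDI change is pre minus post and lifestyle change is post minus pre, so a positive value means improvement on both sides.
- Predictors: "Independent variables were participant sex, age, and lifestyle change score for each lifestyle question". The preceding text lists four areas: "Lifestyle Factor (restful sleep, exercise, mealtime regularity, avoiding dietary triggers".
- Analysis: "Models were constructed and analyzed with the *lmer* and *anova* functions, respectively".

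No coefficient, standard error, confidence interval or effect size is named for these models, and there is no rule for reading a non-significant term. The emmeans step and the false-discovery adjustment are described with the factorial models, before the change-score models are introduced. They apply to significant effects and to pairwise comparisons. The same earlier text makes participant a random factor in all models.

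On numbers, Design and Participants says "Analysis was performed for the 28 participants with completed data sets". No planned sample size, power or precision is stated. At the end of Statistical Methods, "On the DHI, a change of 18 points is considered significant", with 29 points as the HDI counterpart; both are used to classify the change of a single participant.

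**The concern.** These are the only models described that link lifestyle change to symptom change. The question they can address is whether participants who changed a given habit more also improved more, and by how much. An F-test on one degree of freedom does not answer it. An association of greater compliance with greater improvement and one with less improvement give the same F.

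Followed literally, the analysis sorts sleep, meals, exercise and diet into significant and non-significant. At this sample size, a component in the second group could easily be reported as unimportant although the data are compatible with a substantial association.

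**Working it through.** **Inputs from the documents.** 41 enrolled; 7 + 1 + 5 = 13 did not complete; 28 analysed. Four lifestyle areas, plus sex and age. One DHI change and one HDI change per participant.

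**Assumptions not in the documents.** Two-sided 5% level; one question per lifestyle area; and, for the point-scale figures only, the standard deviations (SDs) and collinearity shown in step 5.

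**Plan's own figures.** 41 - 13 = 28; 13/41 = 31.7%; 28/41 = 68.3%. These reproduce. There is no power calculation to reproduce.

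**1. Residual degrees of freedom.** Six predictors and an intercept: 28 - 7 = 21. t(0.975, 21) = 2.080, so the critical F is 2.080² ≈ 4.32.

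**2. Smallest significant partial correlation.** t/√(t² + df) = 2.080/√(4.325 + 21) = 0.413.

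**3. Power for one lifestyle term.** Noncentral F with 1 and 21 df and noncentrality λ = f² × m, where f² = r²/(1 - r²). The two columns are two conventions for m.

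| True partial r | f² | Power, m = 21 | Power, m = 28 |
|---|---|---|---|
| 0.3 | 0.099 | 28% | 36% |
| 0.4 | 0.190 | 48% | 60% |
| 0.5 | 0.333 | 71% | 83% |

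Simulation (4,000 data sets per effect size) gave 29% at 0.3 and 71% at 0.5, close to the m = 21 column.

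**4. What a non-significant estimate leaves open.** Fisher z interval with five other predictors: SE = 1/√(28 - 5 - 3) = 0.224, half-width on the z scale 1.96 × 0.224 = 0.438.

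| Observed partial r | 95% CI |
|---|---|
| 0 | -0.41 to 0.41 |
| 0.2 | -0.23 to 0.57 |
| 0.3 | -0.13 to 0.63 |
| 0.4 | -0.01 to 0.70 |

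All four are below 0.413 and so non-significant. The upper limit reaches 0.5 once the estimate exceeds tanh(atanh(0.5) - 0.438) = 0.11.

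**5. Precision in points per lifestyle step.** Half-width = t × residual SD × √VIF / (item-change SD × √27), where VIF is the variance inflation from the other predictors.

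- Residual SD 20, item-change SD 1.0, VIF 1: 2.080 × 20/√27 = 8.0 points.
- Low end (10, 1.5, 1): 2.7 points.
- High end (25, 0.8, 1.5): 15.3 points.

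The range is thus about 3 to 15 points per step, driven entirely by assumed SDs.

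**6. Sign check.** In a simulated data set of this form, reversing the outcome left F at 6.71 while the slope went from +0.43 to -0.43.

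**7. Can the slopes come from the model as written?** With one change score per participant, a participant random effect cannot be separated from residual error. A test in R confirmed that lme4's lmer stops with an error for this structure, because the number of participants must be smaller than the number of observations. Also, anova on a plain lme4 fit, tested on data with two rows per participant, printed F without a p-value. The figures above therefore refer to ordinary linear regression.

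**8. Do the 18- and 29-point benchmarks work as margins for a slope?** With a half-width of 8 points, a non-significant slope lies within ±8, so its interval lies within ±16. Every non-significant DHI term would exclude 18 and pass as not associated. The same happens at any half-width below 18/2 = 9 (DHI) or 29/2 = 14.5 (HDI).

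**The case against.** The sentence names software functions; it is not a list of outputs. A linear model estimates signed coefficients whether or not the methods text mentions them, and nothing says they would be withheld. That is fair as to intent. The gap is that the text commits to none of them, and the emmeans step would not supply an interval for a non-significant numeric slope.

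A reader might also infer more than the documents support:

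- That the plan treats non-significance as absence of association. It does not say so, and no results or conclusions are given. This is an unguarded risk, not an error already made.
- That anova conveys nothing about size. A partial R² can be recovered from F and its degrees of freedom. Direction, points per step and an interval in points cannot.
- That no non-significant result excludes a large association. An estimate very near zero does exclude 0.5, though not 0.41.
- That the slopes can be read off the models as specified. They cannot until the random effect is removed.
- That the 18- and 29-point benchmarks can decide whether a slope matters. They concern one participant's change in total score, and step 8 shows that using them per step would produce the very over-reading at issue.

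Finally, the stated purpose is the effect of lifestyle modification on symptoms, which the factorial model and the individual-change comparison address. The change-score models are supporting. This limits the weight of the point but does not remove it.

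**Conclusion.** The point holds in this limited form: the stated analysis of the change-score models cannot show the direction, slope or precision of any lifestyle association, and the sample is too small for a non-significant term to be informative in most cases. The threshold of about 0.41 and the power of about 28-36% at a true partial correlation of 0.3 rest on the 28 analysed participants, a two-sided 5% level and one question per lifestyle area; more questions would leave fewer degrees of freedom. The half-widths in points only illustrate scale, because the documents give no SDs for them. This is a worthwhile improvement to a supporting analysis, not a flaw in the main comparison.

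**What to change.** Amend the inter-individual variability paragraph of Statistical Methods as follows.

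1. Fit the DHI and HDI change-score models as ordinary linear regressions, without the participant random effect.
2. For each lifestyle item and each inventory, report the adjusted slope (points of improvement per one-step lifestyle improvement) with its sign and 95% CI.
3. Describe a non-significant term as inconclusive, not as evidence of no association.
4. Do not use the 18- and 29-point benchmarks as margins for per-step slopes; keep them for individual change in total score.

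No new data are needed. The models must be restated and refitted, because the slopes cannot be taken from the mixed models as specified. The downside is wide intervals and more cautious conclusions.
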